3.2 Secondary Objectives & Hypotheses

(1) **Objective:** Based on changes in tumor FDG uptake at 3 weeks, determine which patients have FDG “flare” (an early increase in tumor FDG PET/CT uptake), and assess whether FDG “flare” is predictive of progression-free survival and overall survival in patients with melanoma on pembrolizumab.

Hypothesis: A flare response on FDG PET/CT performed 3 weeks after initiation of pembrolizumab is predictive of progression-free survival and overall survival in patients with melanoma.

(2) **Objective:** To collect tumor tissue pre- and post- treatment with pembrolizumab for correlation with changes in FDG uptake and objective response to therapy, and for studies of mechanism of action of PD-1 blockade with pembrolizumab.

Hypothesis: Treatment with pembrolizumab will result in a measurable change in tumor immune biomarkers, which will correlate with changes in tumor FDG uptake (including a “flare” response) and objective response to therapy, and will contribute to a better understanding of the mechanism of action of pembrolizumab.

(3) **Objective:** To measure immune biomarkers in blood from subjects before and at serial time points after treatment with pembrolizumab, for correlation with changes in FDG uptake and objective response to therapy, and for studies of mechanism of action of PD-1 blockade with pembrolizumab.

Hypothesis: Treatment with pembrolizumab will result in a measurable change in blood immune biomarkers, which will correlate with changes in tumor FDG uptake (including a “flare” response) and objective response to therapy, and will contribute to a better understanding of the mechanism of action of pembrolizumab.

(4) **Objective:** To correlate changes in tumor FDG uptake (including a “flare” response), serum immune biomarkers, and tissue immune biomarkers with objective response to therapy, progression-free survival, and overall survival. Changes in FDG uptake within immune related tissues (lymph nodes, spleen, bone marrow, and thymus) will also be correlated with serum and tissue immune biomarkers, and response.

Hypothesis: Serum and tissue immune biomarkers provide additional predictive value regarding objective response to therapy, progression-free survival, and overall survival when combined with FDG PET/CT imaging data.

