8.0 STATISTICAL CONSIDERATIONS

8.1 Design:

This is a pilot correlative study for patients with metastatic melanoma receiving pembrolizumab on a standard regimen. The intent of this study is to evaluate FDG PET/CT as an early measure of response to immunotherapy. Tumor FDG uptake will be measured at baseline and at 3 and >10 weeks after initiation of pembrolizumab. 30 evaluable patients will be enrolled; evaluable implies that the patient had baseline and week 3 FDG PET/CT scans. This study will also include serum and tissue sampling for immune biomarkers.

8.2 Objectives:

The primary objectives are to:

1. Determine the distribution of changes from baseline in tumor FDG uptake on PET/CT at 3 weeks and >10 weeks after initiation of pembrolizumab.
2. Test for the association between change in tumor FDG uptake on PET/CT at 3 weeks and objective response (RECIST).

The secondary objectives are to:

1. Based on change in FDG uptake at 3 weeks, determine which patients have FDG “flare.”
2. Test for the association between FDG flare (yes/no) and objective response.
3. Test for the association between FDG flare and progression-free and overall survival.
4. Test for correlation between change in FDG uptake and levels of immune biomarkers in serum and tissue.
5. Test for association between changes in immune biomarkers in serum and tissue with objective response, progression-free survival, and overall survival.

8.3 Endpoints:

1. Objective response is defined by RECIST. The clinical evaluation takes place at 3 months per standard pembrolizumab regimens. Patients will be categorized as responders (complete response or partial response) or nonresponders (stable disease or progressive disease).

2. The maximum standardized uptake value (SUVmax) will be analyzed for all tumor sites. Immune-related tissues will be analyzed with SUVmax and SUVmean.
3. Studies have shown that the baseline test/re-test variability is 15-20%. Thus, FDG “flare” will likely be defined by >20% increase in tumor FDG uptake at 3 weeks. This definition may be modified for the observed distribution of changes in tumor FDG uptake on our study.
4. Progression-free and overall survival are defined in Section 4.1.2.
5. Immune biomarkers (see Section 7.1.2.3).

8.4 Plans for Data Analysis:

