This is a pilot correlative study of FDG PET/CT imaging to evaluate early response to immunotherapy. We will first begin with a descriptive analysis. For continuous variables, we will generate graphs and descriptive statistics (e.g., means, standard deviations, medians and inter-quartile range). Categorical variables will be described by frequencies, proportions and 95% exact confidence intervals. Change in tumor FDG uptake will be closely examined. It is likely that change in tumor SUVmax >20% will be classified as a FDG “flare” and the number of patients with a flare will be computed.

Next, associations between change in tumor FDG uptake with clinical outcomes will be conducted. Change in tumor FDG uptake at 3 weeks will be compared between responders and nonresponders by a two sample t-test. Also, objective response rates will be compared between patients with or without FDG “flare” by Fisher’s exact test.

PFS and OS will be estimated by the method of Kaplan and Meier. Median values and 95% confidence intervals will be calculated. PFS and OS will be compared between patients with or without FDG “flare” by the log rank test. Cox regression may be used to assess the effect of continuously scaled measurements of FDG change. For all survival analyses, a landmark analysis will be performed. Here, PFS or OS are defined from a landmark, which is 3 weeks after initiation of pembrolizumab. The landmark method is necessary because the change in tumor FDG uptake is known at 3 weeks. Serum and tissue biomarkers will be correlated with change tumor FDG uptake, using Pearson correlation or Spearman’s correlation, as appropriate. Within-patient pre-/post-treatment changes in biomarkers will be evaluated by paired Student’s t-test or Wilcoxon signed ranks test, as appropriate. We will test for an association between post-/pre-treatment fold change in immune biomarkers in serum and tissue and objective response, progression-free survival, and overall survival using logistic regression (for response) and Cox regression (for time-to-event outcomes) using landmark survival analysis.

8.5 Sample Size Justification:

The target is 30 evaluable patients, which may require up to 35 enrolled patients. Based on our clinical experience, we assume a 50% objective response rate, thus there will be 15

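### Secondary objective 4 in 8.2 pairs FDG change with biomarker levels, and 8.4 names no metric, so no stated analysis tests the change-on-change hypotheses in 3.2(2) and 3.2(3)

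*Combined protocol and SAP*

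**What the plan says.** Section 3.2 states the tissue hypothesis as "Treatment with pembrolizumab will result in a measurable change in tumor immune biomarkers, which will correlate with changes in tumor FDG uptake" and the blood hypothesis as "Treatment with pembrolizumab will result in a measurable change in blood immune biomarkers, which will correlate with changes in tumor FDG uptake". In both, the biomarker side of the correlation is a change.

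Section 8.2, secondary objective 4, reads "Test for correlation between change in FDG uptake and levels of immune biomarkers in serum and tissue". The next item, objective 5, reads "Test for association between changes in immune biomarkers in serum and tissue with objective response, progression-free survival, and overall survival". So adjacent items use *levels* for the FDG correlation and *changes* for the clinical outcomes.

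Section 8.4 has three relevant sentences:

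- FDG correlation: "Serum and tissue biomarkers will be correlated with change tumor FDG uptake, using Pearson correlation or Spearman’s correlation, as appropriate". Neither level nor change is named.
- Biomarker change on its own: "Within-patient pre-/post-treatment changes in biomarkers will be evaluated by paired Student’s t-test or Wilcoxon signed ranks test, as appropriate".
- Clinical outcomes: "We will test for an association between post-/pre-treatment fold change in immune biomarkers in serum and tissue and objective response", and likewise for PFS and OS.

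No time point is given for the biomarker in the FDG correlation. Footnote 3 of the flow chart in 6.1 lists blood draws at weeks 0, 1, 3, 6, 9, 12 and 15 and at 1 year.

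**The concern.** Each hypothesis has two parts: treatment changes the biomarker, and that change moves with FDG uptake. The paired tests in 8.4 cover the first part. For the second part, the only stated rule is the one in 8.2, and it uses levels.

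A level is the pre-treatment value plus whatever treatment added. A patient whose tumor was already inflamed before the first dose may have a high level without any treatment-induced change. The rationale in 4.1 attributes the flare to immune cells drawn in by therapy, and the tissue is collected to explain the FDG changes. A positive level correlation could reflect pre-existing inflammation, yet be reported as support for that mechanism. A null level correlation would not refute it.

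Because 8.4 leaves the metric open and there are up to eight blood time points, the choice could also be made after the data are seen.

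**Working it through.** **1. The plan's own figures.** The plan gives no power, effect size, significance level or number of pairs for the FDG-biomarker correlation. Its only power figure, in 8.5, is 84% for the responder comparison (15 against 15, 1.0 SD, one-sided 5%). The noncentral t with 28 df gives 84.8%, so that figure reproduces. It has no bearing on this point.

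**2. Hypothesis against analysis.**

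| Place | Biomarker quantity | Set against |
|---|---|---|
| 3.2(2), 3.2(3) hypotheses | change | FDG change |
| 8.2 objective 4 | level, time point not given | FDG change |
| 8.2 objective 5 | change | response, PFS, OS |
| 8.4 correlation | not specified | FDG change |
| 8.4 paired tests | change | zero |
| 8.4 logistic and Cox models | post/pre fold change | response, PFS, OS |

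The pairing in the first row appears in no later row.

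**3. Size of the effect on power.** All of these inputs are assumptions: n = 30 pairs, two-sided 5%, true correlation r = 0.50 between biomarker change and FDG change, and FDG change unrelated to the pre-treatment level. Power is by Fisher's z: Φ(√(n−3)·atanh(r) − 1.96), plus a negligible opposite tail.

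Using change: √27 × atanh(0.50) = 5.196 × 0.549 = 2.854, and Φ(2.854 − 1.96) = 81.4%.

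*Model A: change independent of the pre-treatment level.* With s = SD(change)/SD(pre), r(post level) = r × s/√(1+s²).

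| s | r(post level) | Power, n = 30 |
|---|---|---|
| 0.5 | 0.224 | 21.9% |
| 0.75 | 0.300 | 36.3% |
| 1 | 0.354 | 48.4% |
| 2 | 0.447 | 70.6% |

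*Model B: equal pre and post variances, pre/post correlation ρ.* Here r(post level) = r × √(2(1−ρ)).

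| ρ | r(post level) | Power, n = 30 |
|---|---|---|
| 0.3 | 0.592 | 94.2% |
| 0.5 | 0.500 | 81.4% |
| 0.7 | 0.387 | 56.5% |
| 0.8 | 0.316 | 39.8% |
| 0.9 | 0.224 | 21.9% |

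A simulation of Model B with 5,000 replicates at ρ = 0.3, 0.5, 0.8 and 0.9 agreed: 94%, 83%, 40% and 22% for the post level, and 81% to 83% for change. If *levels* means pre-treatment levels, power equals the type I error, about 5%.

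**4. Fewer pairs.** With 15 pairs, change has 48% power. The Model B post level has 65%, 48%, 29%, 21% and 12% for the same five values of ρ.

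**The case against.** Four points can be made for the plan.

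First, a reader might infer that 8.4 also plans a level correlation. It does not say so. It is silent on the metric, and the correlation could be run on change under its present text. This stands: 8.4 is unspecified, not wrong. But 8.2 is the only place that names a metric, and 8.4 does not override it.

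Second, a reader might infer that using levels throws away most of the power. The documents do not support this. The result depends on a pre/post correlation, or an SD ratio, that they never give. Under equal variances there is no loss at ρ = 0.5 and a gain below it. With r = 0.50 and n = 30, power falls below half of the change-based power only from ρ of about 0.80. This stands in full, so the case for the fix does not rest on power.

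Third, the objective sentences in 3.2 speak only of collecting tissue and measuring blood markers for correlation with FDG change, and levels would serve those. This stands for the objectives but not for the hypotheses, which name change.

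Fourth, change needs pairs. Pre-therapy tissue exists only if a biopsy was done for clinical care, either biopsy may be missing, and the post-therapy biopsy may come from another lesion. This is a genuine cost. It is a reason to keep levels as a labelled supplement, not as the test of a change hypothesis. This is also a secondary analysis in a pilot, with some assays dependent on further funding, which limits its weight.

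**Conclusion.** The mismatch is real and can be read directly from the text. Hypotheses 3.2(2) and 3.2(3) are about change on change, 8.2 objective 4 names levels, and 8.4 names nothing. The *measurable change* part of the hypotheses is tested; the part linking that change to FDG change is not. This conclusion needs no numerical assumption.

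The effect on power cannot be fixed from the documents. Against 81% for change (n = 30, two-sided 5%, r = 0.50, FDG change unrelated to the pre-treatment level), the post-treatment level gives 22% to 71% under Model A and 94% down to 22% under Model B. The analysis should be corrected because it answers a different question, whichever way the power moves. It is worth correcting before analysis, but it does not touch the primary comparison.

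**What to change.** In 8.2 objective 4 and in 8.4, state that change in tumor FDG uptake at 3 weeks is correlated with within-patient biomarker change, log(post/pre). This is the log of the fold change that 8.4 already uses for the outcome analyses. Name the pre-treatment sample and one post-treatment time point for blood. The week 3 draw is a natural candidate, since the scan is nominally at 3 weeks. For tissue, name the post-therapy biopsy. Keep any correlation with pre- or post-treatment levels as a separate analysis labelled supplementary, and do not offer it as a test of 3.2(2) or 3.2(3).

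Report the number of pairs for each correlation and, for tissue, whether both biopsies came from the same lesion.

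The cost is a change of wording, with no added visit, sample or patient. Patients without a pair drop out of this correlation. Tissue pairs may be few or drawn from different lesions, and with 15 pairs even the change-based test has only 48% power at an assumed r of 0.50. The tissue result should therefore be presented as an estimate with its confidence interval.

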7.1.4.2 Clinical Follow-up

Clinical follow-up may include standard of care imaging, tumor markers and standard visits with a treating physician at intervals standard for metastatic melanoma follow-up after the start of new treatment, and usually at the time of symptomatic progression. The timing of clinical visits will be determined by the treating physician and is not mandated by this study.

Information will be collected through medical record review to assess for status of disease and the date of progression will be documented at the time of clinical progression. Clinical follow up for overall survival, by medical record review, will continue until loss to follow up or death. For those whose are cared for by a non-UPHS clinician during this period, this clinician will be contacted by phone for follow-up. The patients may also be contacted by phone for follow-up.

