7.1.5 Image Interpretation

Static images will be reconstructed using standard procedure and analyzed by visual inspection and standardized uptake value (SUV) analysis. The tumor avidity, as estimated by the SUVmax, of the primary tumor and up to 5 metastatic lesions will be measured on each FDG PET/CT scan. Patients will be grouped into responders (partial/complete response) and nonresponders (stable disease or progressive disease) based on RECIST. Patients will also be grouped based on a positive flare response (greater than 20% increase in SUVmax) or negative flare response (less than 20% increase in SUVmax). An exploratory tumor-by-tumor FDG PET/CT response analysis will be performed for the primary tumor and up to 5 metastatic lesions in each patient. Changes in FDG uptake within immune related tissues (lymph nodes, spleen, bone marrow, and thymus) will also be measured as an exploratory objective using SUVmax and SUVmean.

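### Does leaving the 20% FDG flare cut-off open to change from the study's own uptake data undermine the flare tests?

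*Combined protocol and SAP*

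**What the plan says.** Three places in the combined protocol and SAP define flare.

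- Section 7.1.5 (Image Interpretation) states it without reservation: "positive flare response (greater than 20% increase in SUVmax) or negative flare response (less than 20% increase in SUVmax". A rise of exactly 20% falls in neither group.
- Section 8.3 (Endpoints) says flare "will likely be defined by >20% increase in tumor FDG uptake at 3 weeks", anchoring 20% to a test/re-test variability of 15 to 20%, and then adds "This definition may be modified for the observed distribution of changes in tumor FDG uptake on our study".
- Section 8.4 (Plans for Data Analysis) keeps the provisional tone: "It is likely that change in tumor SUVmax >20% will be classified as a FDG" flare.

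Section 8.4 also gives an order of work. It opens with "We will first begin with a descriptive analysis", and the flare count belongs to that step. Only then comes "Next, associations between change in tumor FDG uptake with clinical outcomes will be conducted". The flare split is used in a Fisher test for objective response and in log rank tests from a 3-week landmark: "PFS and OS will be compared between patients with or without FDG" flare. The primary comparison is a two-sample t-test on continuous change in uptake.

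**The concern.** A threshold that may be revised after the data are in is a familiar source of false positives. Section 3.2 makes flare as a predictor of PFS and OS its first secondary hypothesis, and the log rank test of that hypothesis depends on where the line is drawn. No section requires the cut-off to be settled and dated before response, PFS or OS are joined to it.

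The calendar adds to the worry. The full uptake distribution exists only after the last week-3 scan, near the end of a year's accrual. By then many outcomes are on file, since under Section 7.1.4.2 "the date of progression will be documented at the time of clinical progression". If the cut-off moved, a reader could not tell from the plan alone whether uptake or outcome had moved it. A positive flare result might then be discounted.

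**Working it through.** **1. The plan's own figure.** Section 8.5 claims 84% power for 15 versus 15 patients, a 1.0 SD difference and a one-sided 5% t-test. The noncentrality is 1.0 × √(15/2) = 2.74 on 28 degrees of freedom. The exact noncentral t gives 84.8%, so the claim reproduces. No flare cut-off enters it.

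**2. Outcomes known when the uptake distribution is complete.** Assume uniform entry over 52 weeks and a last early scan at week 55 (52 + 3). Follow-up then runs evenly from 3 to 55 weeks.

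- With an assumed exponential PFS median of 26 weeks, λ = ln 2/26 = 0.02666. The event-free proportion is (e^(−3λ) − e^(−55λ))/(52λ) = (0.923 − 0.231)/1.386 = 0.50. About 15 of 30 patients would have had an event. Medians of 52 to 20 weeks give 31-58%.
- Past a 3-month response assessment (Section 8.3): (55 − 13)/52 = 81%. Past a 6-month one (Section 4.1.2.1): (55 − 26)/52 = 56%.

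So outcomes would exist by then. Whether they matter depends on whether they are used.

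**3. Why a cut-off chosen from uptake alone is harmless.** Under the null, uptake change is independent of outcome. A cut-off computed only from the uptake values is fixed once those values are given, and so is the grouping. The test then compares two groups formed without reference to outcome, as it does with 20% set in advance.

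**4. Size by simulation.** All runs have n = 30, no true association and a two-sided 5% level. That level is an assumption, because the plan states none for the Fisher or log rank tests.

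- Set A: percent change N(5,30), N(0,40) or N(10,25); exponential PFS with median 26 weeks; censoring uniform over 52-104 weeks; week-3 landmark; at least 3 patients per group for the searched cut-offs; 10,000 runs each.
- Set B: N(0,30), N(0,40) or N(10,40); exponential survival with uniform censoring; 6,000 runs each.

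Log rank false-positive rates:

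| How the cut-off is set | Set A | Set B |
|---|---|---|
| Fixed at 20% | 6.0-6.2% | 5.6-6.5% |
| From uptake alone | 5.6-6.7% | 5.6-5.7% |
| Best p of 3 cuts (15-25%) | 10-11% | 9.7-11.9% |
| Best p of 5 cuts (10-30%) | 13-16% | 13.1-16.5% |
| Best p of 7 cuts (10-40%) | 17-20% | not run |

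The uptake-only rules were the median, upper tertile and largest gap in Set A, and the median in Set B. With OS-like events in Set A (median 104 weeks, about 39% events), the five rows are 5.1-5.8%, 4.9-5.5%, 10%, 12-14% and 15-17%.

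Fisher test in Set B: 2.6-2.8% at fixed 20%, 1.5-1.7% at the median, and 6.5-7.0% for the best of 5 cuts.

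**5. What a rigid 20% could cost.** If change were N(−10,20), the share above 20% would be P(Z > 1.5) = 0.067, about 2 of 30 patients, and the split would tell little. The permission in Section 8.3 covers that case.

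**The case for a change.** The strongest reply is that an order of work is not a lock. Section 8.4 sets no date, gives no rule for choosing a new cut-off and does not keep outcomes from whoever chooses. About half the patients may have had a PFS event by then, flare is in the study's abbreviated title, and the continuous alternative (Cox regression) is only optional. One sentence would settle the matter.

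Much of this stands as description. There is no dated lock, and the wording of 7.1.5, 8.3 and 8.4 does not match. It does not stand as a defect of method:

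- The inflated rates need the team to leave the one basis that Section 8.3 names. Their size is set by the assumed search: the same null gives 10-11% with 3 cuts and about 43% with any cut between the 10th and 90th percentiles.
- The absence of blinding in the Trial Summary describes a single cohort without treatment groups. It does not say that whoever sets the cut-off works from outcome data.
- All three sections name 20%, so a move away from it would be visible and a reader could ask for the 20% result.
- A sentence allowing an uptake-only change before linkage would document the choice but would not blind it. It restates what the plan already implies.

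**Conclusion.** The concern does not call for a change. Followed as written, the plan holds the log rank error at 5.6-6.7%, no different in practice from the 6.0-6.2% of a fixed 20% cut-off, and the second set of assumptions agrees. The roughly 10-20% range describes a departure from the plan, and it depends on assumed grids, spreads, event rates and a two-sided 5% level that the documents do not supply. The two primary objectives do not use the cut-off.

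Letting the observed distribution inform a provisional threshold is a fair trade-off in a self-described pilot whose first primary objective is to describe that distribution. A hard lock at 20% shows no gain in these figures and could leave an uninformative split. The mismatch between Section 7.1.5 and Sections 8.3 and 8.4, and the unassigned value of exactly 20%, are clerical. An analyst would read flare as above 20% and non-flare as 20% or below, note when the cut-off was settled, and show the 20% result beside any other.

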responders and 15 nonresponders. A comparison of change in FDG SUV at 3 weeks between responders and nonresponders, will have 84% power to detect a 1.0SD difference in mean values, using 1-sided two sample t test at a 5% significance level. The 1-sided test is justified, since responders are expected to have greater changes in FDG SUV.

8.6 Study Duration:

This study will enroll 30 evaluable patients over 1 year.

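### Fisher's exact test for response by FDG flare (a secondary comparison) is valid but conservative in 30 patients; Boschloo's exact test holds the same level, is never less powerful, and gains from nothing to about 15 points of power depending on the flare split

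*Combined protocol and SAP*

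**What the plan says.** Section 8.2 lists this comparison as the second secondary objective: "Test for the association between FDG flare (yes/no) and objective response". Section 8.4 gives the method: "objective response rates will be compared between patients with or without FDG" flare by Fisher's exact test. No significance level, sidedness or power is stated for it.

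On size, Section 8.5 says: "The target is 30 evaluable patients, which may require up to 35 enrolled patients". It continues "we assume a 50% objective response rate", which gives 15 "responders and 15 nonresponders". The only level and sidedness in the plan belong to the primary comparison of mean FDG change, "using 1-sided two sample t test at a 5% significance level", which "will have 84% power to detect a 1.0SD difference in mean values".

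The number of patients expected to flare is not given anywhere. Flare is provisionally an increase above 20%, and Section 8.3 adds: "This definition may be modified for the observed distribution of changes in tumor FDG uptake on our study".

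**The concern.** Fisher's test conditions on both margins of the 2x2 table. This design fixes neither in advance: the number of flare patients and the number of responders are both observed. Given both margins, only a few p-values can occur in 30 patients, so the chance of a p-value at or below 5% under no association is usually well under 5%. The unused part of the error allowance is lost power.

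Boschloo's test takes the Fisher p-value as its statistic and refers it to the unconditional distribution, maximised over the unknown common response rate. It is exact in the same sense as Fisher's test. What is at stake is the chance of detecting a link between flare and response in a small study whose size cannot absorb avoidable losses.

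**Working it through.** **Inputs.** N = 30 evaluable, 50% response and 15 v 15 by response come from Section 8.5, and the test from Section 8.4. Assumptions: a 5% level, taken two-sided and then one-sided; flare splits as listed; response rates as listed.

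**The plan's own power figure.** For the t-test with 15 per group and a 1.0 SD difference, the noncentrality is 1/√(2/15) = 2.739 with 28 degrees of freedom. One-sided 5% power is 84.8%, against the plan's 84%, so the figure is reproduced. It applies to the t-test only. There is no stated power for Fisher's test to reproduce.

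**Why Fisher's test is conservative here.** Take a 15/15 flare split and 18 responders in all. There are C(30,18) = 86,493,225 arrangements.
- 12 v 6 responders or more extreme in that direction: 455×5005 + 105×3003 + 15×1365 + 1×455 = 2,613,520, or 0.0302. Doubled by symmetry, p = 0.060.
- 13 v 5 or more extreme: 315,315 + 20,475 + 455 = 336,245, or 0.0039. Doubled, p = 0.008.

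With these margins the attainable p-values jump from 0.008 to 0.060, so a nominal 5% test runs at 0.8%. Averaging over the possible numbers of responders gives the true error rate.

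**Method for the true error rate and power.** For n1 flare and n2 = 30 − n1 non-flare patients, every table (a, b) of responders has probability Bin(a; n1, p1) × Bin(b; n2, p2). Size is the maximum rejection probability over p1 = p2 from 0.001 to 0.999. Power is the rejection probability at the stated p1 and p2. The Boschloo rejection region adds tables in order of their Fisher p-value for as long as the maximum size stays at or below 5%.

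**Results, two-sided 5%, response 80% (flare) v 35% (no flare).**

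| Flare / no flare | Max. size, Fisher | Max. size, Boschloo | Power, Fisher | Power, Boschloo |
|---|---|---|---|---|
| 15/15 | 1.8% | 4.3% | 56% | 71% |
| 12/18 | 3.1% | 4.95% | 59% | 70% |
| 10/20 | 3.3% | 4.1% | 55% | 64% |
| 9/21 | 3.9% | 4.7% | 61% | 61% |
| 8/22 | 3.8% | 4.6% | 58% | 58% |
| 6/24 | 2.4% | 3.95% | 40% | 49% |

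Over splits from 3/27 to 15/15, Fisher's maximum size is 1.7% to 3.9% two-sided and 1.7% to 2.9% one-sided. Boschloo's never exceeds 5%.

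**Holding overall response at the plan's 50%.** The 80% v 35% scenario implies (80 + 35)/2 = 57.5% overall at 15/15, so scenarios that average to 50% were also run. Two-sided power goes from 43.4% to 59.0% at 15/15 (70% v 30%), from 50.0% to 62.6% at 12/18 (75% v 33%), and from 73.0% to 73.3% at 9/21 (85% v 35%).

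**Treating the number of flare patients as random.** At 80% v 35%, two-sided, the average gain is about 6-9 points for true flare rates of 20% to 50%. At a 10% flare rate it is about 11 points, but power is then only 18% to 29%.

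**One-sided 5%.** At the six tabulated splits and 80% v 35%, the gains are about 9-15 points, including 11 to 14 points at 8/22 and 9/21.

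**Why Boschloo cannot lose power.** For any cut-off u, the probability under no association that the Fisher p-value is at most u is an average, over the number of responders, of conditional probabilities that are each at most u. The unconditional maximum is therefore also at most u. So Boschloo's p-value never exceeds Fisher's when the ordering is the same, and every table that Fisher's test rejects is also rejected by Boschloo's.

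**Example.** 12/15 v 6/15 responders gives Fisher p = 0.060 and Boschloo p = 0.030. The conclusion at 5% depends on which test is named, so the choice has to be made before the data are seen.

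**The case against.** The best case for leaving the plan alone is that nothing in it is wrong. Fisher's test controls the error rate, and conditional against unconditional exact testing is an old choice between legitimate methods. The comparison is secondary in a pilot study that begins with description. The only powered test of early FDG change against response is the t-test on the continuous measure, and the flare hypothesis in Section 3.2 concerns progression-free and overall survival. No decision rule and no part of the sample size rests on this p-value. The gain may also be nil: at 8/22 or 9/21, two-sided, it is under half a point.

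All of that stands, and it sets the weight of the point. It does not remove it, because the replacement has the same guarantee, cannot do worse, and costs almost nothing. The argument for conditioning has little force in a design that fixes neither margin.

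Three further objections were weighed. Section 8.4 lists many tests without multiplicity control, and a less conservative test uses more of its error allowance; but the lack of control applies equally to Fisher's test, and accidental conservatism is a poor substitute for it. The flare cut-off may be modified; Section 8.3 ties this to the distribution of uptake and not to response, but if it were tuned to response neither exact test would hold 5%. Two-sided Boschloo tests come in slightly different versions; this is true, and the version must be named.

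**Conclusion.** The point holds as an optional improvement. At an assumed 5% level, Fisher's test in 30 patients has a maximum true size of about 2-4% two-sided or 2-3% one-sided. Boschloo's test stays within 5% and is never less powerful. In the tabulated scenarios the two-sided gain runs from essentially nothing to about 15 points, and the one-sided gain is about 9-15 points.

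These sizes rest on assumptions that the plan does not supply: the flare split, the two response rates, and a 5% level carried over from the t-test. They also need a flare cut-off set without reference to response.

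Three stronger readings might be inferred, and the documents support none of them:
- That Fisher's test is an error. It is valid and only conservative.
- That this is the study's main test, or that its conservatism undermines the planned size. Section 8.2 makes it secondary, and Section 8.5 sizes the study on the t-test alone.
- That about 15 points is the gain to expect. It is close to the best two-sided case among the tabulated splits, and the plan gives no flare rate that would favour it.

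**What to change.** In Section 8.4, replace Fisher's exact test for response by flare status with Boschloo's exact test, before outcome data are seen. In the same place:
- State alpha and sidedness for this comparison.
- If it is two-sided, name the version: ordering on the two-sided Fisher p-value, or doubling the one-sided Boschloo p-value.
- Report the difference in response rates with an exact unconditional 95% confidence interval built to agree with that test, so that interval and p-value cannot point in different directions.
- State that the flare cut-off will be set without reference to response.

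The cost is a few lines of text. The test is in standard software and needs no more patients or data. The drawbacks are that it is less familiar to readers than Fisher's test and that its version must be specified.
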